## 2. Protocol Synopsis

REPRISE II: Repositionable Percutaneous Replacement of Stenotic Aortic Valve through Iplantation of Lotus™ Valve System – Evaluation of Safety and Performance	
Objective(s)	To evaluate the safety and performance of the Lotus™ Valve System for transcatheter aortic valve replacement (TAVR) in symptomatic subjects with severe calcific aortic stenosis who are considered high risk for surgical valve replacement.
Intended Use	The Lotus Valve System is intended to improve aortic valve function for symptomatic subjects with severe calcific aortic stenosis (aortic valve area [AVA] of <1.0 cm  or index of <0.6 cm  /m  ) who are at high risk for standard surgical valve replacement.
Test Device	The Lotus Valve System consisting of two main components: 
 
- a bioprosthetic bovine pericardial aortic valve
 
- a delivery system.
 

Device Sizes	The sizes of the Lotus Valve used in this study will include the 23 mm diameter size suitable for subjects with aortic annulus diameter between ≥20 mm and ≤23 mm, and the 27 mm diameter size suitable for aortic annulus diameter between ≥23 mm and ≤27 mm.  Note: The commercially approved Lotus Introducer Set will be used as an accessory to the Lotus Valve System during the procedure. The Lotus Introducer provided for use with the 23 mm valve will be suitable for use in subjects with femoral artery lumen diameter ≥6.0 mm, and the Lotus Introducer provided for use with the 27 mm valve will be suitable for use in subjects with femoral artery lumen diameter ≥6.5 mm.
Comparator	For the device performance primary endpoint, a performance goal (PG) based on the 30-day mean aortic valve pressure gradient derived from published literature will be used as the comparator for analysis.  For the primary safety endpoint, a performance goal (PG) based on 30-day all-cause mortality data derived from published literature will be used as the comparator for analysis.
Study Design	The REPRISE II clinical study is a prospective, single-arm, multicenter study designed to evaluate the safety and performance of the Lotus Valve System for TAVR in symptomatic subjects who have severe calcific aortic valve stenosis and who are at high risk for surgical aortic valve replacement

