Sample Size Parameters	
 
• Expected 30-day all-cause mortality rate = 9.8%
 
• Performance goal (PG) = 16 % (expected rate of 9.8% + testing margin of 6.2%)
 
• Test significance level (<math>\alpha</math>) = 0.025 (1-sided)
 
• Power (<math>1 - \beta</math>) = 80%
 
• Expected rate of attrition = 2%
 
• Planned enrollment of up to 250 subjects (main trial cohort enrollment of 120 subjects plus extended trial cohort enrollment of 130 subjects)
 
 
Note: The expected 30-day all-cause mortality rate is assumed to be 9.8% based on a literature review of studies evaluating the Medtronic CoreValve System and the Edwards Lifesciences SAPIEN Transcatheter Heart Valve System.

Success Criteria	
If the P value from the one-sample z-test is <math><0.025</math>, it will be concluded that the primary safety endpoint for the Lotus Valve is less than the PG. This corresponds to the one-sided upper 97.5% confidence bound of the observed 30 day mortality rate being <math><16</math> %.

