trials. Through 2-year follow-up in the PARTNER US IDE trial there have been significant reductions in mortality and repeat hospitalization rates compared to standard medical therapy in subjects unsuitable for SAVR^29, and similar mortality rates compared to surgical valve replacement in high-surgical-risk subjects. An expert consensus document on TAVR was recently published.

Table 4.1-1 summarizes the peri-operative event rates through 30 days post-procedure from several TAVR studies that enrolled similar subjects as those planned for this study, as well as the results from the inoperable (Cohort B) and high risk (Cohort A) subjects with severe aortic stenosis enrolled in PARTNER. A more detailed summary of the available literature is presented in the Investigator Brochure.

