**Table 4.1-1: Events from Peri-Operative to 30 Days (Transfemoral Approach)**

Study	Device/N	Death	MI	Major Stroke	Bleeding	Acute Kidney Injury	Vascular Complications
Webb, et al. 2006 	EW/18	11%	0%	0%	N/A	N/A	N/A
Webb, et al. 2007 	EW/50	12%	2%	4%	N/A	N/A	N/A
Webb, et al. 2009 	EW/113 a	8%	N/A	5.3%	11.6%	4.4%	8%
Osten, et al. 2010 	EW/16	6%	0%	6%	13%	0%	13%
Rodés-Cabau, et al. 2010 	EW/168 a	9.5%	0.6%	3.0%	N/A	N/A	N/A
Thomas, et al. 2010 	EW/463 a	6.3%	N/A	2.4%	9.9%	1.3%	22.9%
Leon, et al. 2010 	EW/267 b	5%	0%	5%	16.8%	1.1%	16.2% c 30.7%
Smith, et al. 2011 	EW/244 a,d	3.4%	0%	3.8%	9.3%	2.9%	14% c 22.7%
Lefèvre, et al. 2011 	EW/55	8.2%	3.3%	3.3%	23.5%	0%	28.4%
Grube, et al. 2006 	CV/25	20%	0%	4%	N/A	N/A	N/A
Grube, et al. 2007 	CV/86	12%	1%	10%	N/A	N/A	N/A
Piazza, et al. 2008 	CV/646	8%	0.6%	1.9% e	N/A	N/A	1.2%
Baan, et al. 2010 	CV/30	20%	0%	0%	N/A	N/A	N/A
Munoz-Garcia, et al. 2012 	CV/133 f	4.5%	0.8%	1.5%	N/A	N/A	2.2% c
Bullesfeld, et al. 2011 	CV/72 b,d,g	18.1%	5.6%	8.3% e	N/A	N/A	N/A
Buchanan, et al.	CV,	4.7%	1.3%	1.0%	33.1%	10.2% h	15.7% c

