#### 12.1.1.3. Primary Safety Endpoint

Subsequent to the enrollment of the main trial cohort for device performance assessment (see Section 12.1.1.2), up to 130 more subjects will be enrolled in the extended trial cohort to perform a statistically powered assessment of the primary safety endpoint. The null and alternative hypotheses for the primary safety endpoint are as follows.

$$H_0: \text{Mortality}_{30D} \geq PG$$

$$H_1: \text{Mortality}_{30D} < PG$$

where  $\text{Mortality}_{30D}$  is the 30-day all-cause mortality rate for the Lotus Valve and PG is the performance goal.

Testing will be done for the primary safety endpoint as described in the statistical analysis plan. A one-sample  $z$ -test will be used, the  $z$ -test statistic is  $z = \frac{P_{30D} - PG}{s_p}$ ,

where

$P_{30D}$  is the sample 30-day all-cause mortality rate,

$PG$  is the performance goal,

$s_p = \sqrt{\frac{P_{30D}(1 - P_{30D})}{N}}$  is the sample standard error,

$N$  is the sample size.

A sensitivity analysis (tipping-point analysis) will be performed to assess the impact of subjects with inadequate follow-up (i.e., missing data) on the primary safety endpoint and to assess the robustness of the conclusion of the primary analysis.

The sample size calculation for the primary safety endpoint is based on the following assumptions.

- Expected 30-day all-cause mortality rate = 9.8%
- Performance goal (PG) = 16 % (expected rate of 9.8% + testing margin of 6.2%)
- Test significance level ( $\alpha$ ) = 0.025 (1-sided)
- Power ( $1 - \beta$ ) = 80%
- Expected rate of attrition = 2%

If the  $P$  value from the one-sample  $z$ -test is  $<0.025$ , it will be concluded that the primary safety endpoint for the Lotus Valve is less than the PG. This corresponds to the one-sided upper 97.5% confidence bound of the observed 30-day mortality rate being  $<16\%$ .

The expected rate of 9.8% for 30-day all-cause mortality is based on a literature review. Given the above assumptions, 233 subjects will be required. In order to account for a 5% expected rate of attrition, a total of 250 subjects is required for the planned hypothesis testing.

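### Is the 9.8% expected mortality behind the 16% safety goal contradicted by the studies cited for it?

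*Combined protocol and SAP*

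**What the plan says.** Section 12.1.1.3 lists the planning assumptions for the safety endpoint, among them "Performance goal (PG) = 16 % (expected rate of 9.8% + testing margin of 6.2" points). Its closing paragraph gives the source in one sentence, "The expected rate of 9.8% for 30-day all-cause mortality is based on a literature review", with a citation to references 8-13, 16-18, 20, 22, 24-28 and 32-37. The synopsis gives the same figure and describes the review in terms of two marketed valves: "The expected 30-day all-cause mortality rate is assumed to be 9.8% based on a literature review of studies evaluating the Medtronic CoreValve System". SAPIEN, the Edwards valve, is named there as the second.

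Under Comparator, the synopsis says that "a performance goal (PG) based on 30-day all-cause mortality data derived from published literature will be used as the comparator for analysis".

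Table 4.1-1 lists size and 30-day deaths for the same 22 references. Section 4.1.1 says that the table "summarizes the peri-operative event rates through 30 days post-procedure from several TAVR studies that enrolled similar subjects as those planned for this study", together with two cohorts of a randomised programme. It adds: "A more detailed summary of the available literature is presented in the Investigator Brochure".

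Neither Section 12.1.1.3 nor the synopsis states which rates were averaged, how they were weighted, or why the margin is 6.2 points.

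**The concern.** In a single-arm trial the performance goal is the only comparator, so a pass means no more than the goal does. Here the goal is a base rate plus a margin, and any excess in the base raises the goal by the same amount, in the lenient direction. The citation list matches Table 4.1-1 reference for reference, so a reader can test the base rate, and the obvious summaries of the full table all come out lower. If the base were really 8.1%, the same 6.2-point margin would give a goal of 14.3% instead of 16%. A device with a true mortality of 14.3% would then have some chance of passing a goal that it should only just fail. With no stated derivation, 9.8% can look like an error or a favourable choice.

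**Working it through.** **The plan's own sum.** 9.8% + 6.2 points = 16.0%. This is correct.

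**Inputs.** Number of patients and 30-day death rate for each reference in Table 4.1-1. Reference 37 reports its two devices separately (133 patients at 8%, 99 at 6%). Combined, this is (133 × 8% + 99 × 6%)/232 = 7.15%. Reference 10 is taken as 73 + 82 = 155 patients at 12%.

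**Summaries of all 22 rows.**

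- Patient-weighted: sum of (patients × rate) / sum of patients = 565.9/6,953 = 8.14%.
- Simple average: 209.15/22 = 9.51% (standard error 1.03 points).
- Random effects (DerSimonian-Laird, logit scale): 8.35%, 95% interval 7.03% to 9.89%.

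So 9.8% is higher by 1.7, 0.3 and about 1.4 points respectively. It lies inside the random-effects interval and well within one standard error of the simple average.

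**A simple rule that gives 9.8%.** The synopsis speaks of studies evaluating the two named systems. Take every rate in Table 4.1-1 that belongs to one device:

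- Edwards, nine rows: 11 + 12 + 8 + 6 + 9.5 + 6.3 + 5 + 3.4 + 8.2 = 69.4.
- CoreValve, six rows: 20 + 12 + 8 + 20 + 4.5 + 18.1 = 82.6.
- Reference 37, reported by device: 8 + 6 = 14.

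The total is 166.0 over 17 rates, and 166.0/17 = 9.76%, which rounds to 9.8%. The only rows left out are the six that print one rate for a mix of both devices. The documents do not say that this rule was used. It does show that the figure can be obtained from the cited table by an unforced choice.

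**What the base rate does to the planned test.** Section 12.1.1.3 uses z = (p − 0.16)/√(p(1 − p)/N), with the observed p in the standard error, and passes if the one-sided P is below 0.025, that is, z < −1.96.

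- N = 250, 29 deaths: p = 0.116, standard error 0.02025, z = −2.17, pass. With 30 deaths, z = −1.95, fail.
- N = 245 (250 less the 2% attrition in the assumption list), 29 deaths: p = 0.1184, standard error 0.02064, z = −2.02, pass. With 30 deaths, z = −1.79, fail.

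The test therefore passes with at most 29 deaths at either size. Power is the binomial probability of 29 or fewer deaths:

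| True mortality | N = 245 | N = 250 |
|---|---|---|
| 9.8% | 87.9% | 85.6% |
| 9.5% | 90.9% | 89.0% |
| 8.4% | 97.6% | 96.9% |
| 8.1% | 98.4% | 98.0% |

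Power exceeds the stated 80% at every candidate base rate. A lower true rate only raises it.

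**Size of the possible leniency.** Measured from the full-table summaries, the 16% goal lies 6.5 points (simple average), about 7.6 (random effects) or 7.9 (patient-weighted) above the base, against the stated 6.2. At a true mortality of 14.3% and N = 250, the chance of 29 or fewer deaths is about 13%.

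**The case for a change.** The strongest case for a change is that a literature-derived goal should be traceable to its literature. The citation list points to all 22 studies, not to a subset, and no summary of the full set that was tried reaches 9.8%. The single-device average is itself a reconstruction. Another route to the figure is to drop reference 28, the study that supplies the high-risk cohort in "results from the inoperable (Cohort B) and high risk (Cohort A) subjects with severe aortic stenosis enrolled in PARTNER": (209.15 − 3.4)/21 = 9.80%. That would remove patients of the very kind this trial enrols, and a reader cannot tell which route was taken. Stating the rule would cost a sentence.

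Part of this stands: the derivation and the reason for the margin are not written down. The rest is weaker. The protocol calls 9.8% an expected rate based on a review, and the synopsis calls it assumed. Neither presents it as a pooled estimate. Patient-weighting lets one registry of 2,361 patients supply about a third of the weight (2,361/6,953 = 34%). A simple average gives a study of 16 the same say as that registry. Random effects lies between the two in this table. Competent statisticians would differ on the choice, so replacing 9.8% with one of these figures would not correct an error. The table also mixes access routes, as its footnotes show, and the fuller literature summary is in the Investigator Brochure, which was not available here.

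**Conclusion.** The concern does not call for a change. The cited table yields 8.1% to 9.5% under the three full-set summaries above and 9.76% under a plain single-device average, so 9.8% is untraced as written but not contradicted. The excess is 0.3 to 1.7 points in an assumed planning rate. The 16% goal is a fixed, pre-specified number, and an explanatory sentence would alter neither it nor the z-test, the sample size or the result. A reader who wants to judge how demanding 16% is can do so from Table 4.1-1, which prints every rate needed.

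This rests on the rates and denominators as printed in Table 4.1-1, on the planned test with the sample standard error, and on 245 to 250 evaluable patients. Section 12.1.1.3 also gives attrition as 5% in its closing paragraph; that is a separate matter and does not affect the base rate.

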#### 12.1.1.4. Statistical Methods

All subjects who are enrolled will be eligible for evaluation. Handling of dropouts and missing data will depend on their frequency and the nature of the outcome measure. The distribution of prognostic factors between subjects with and without data will be examined. Methods to eliminate or minimize bias will be implemented and described completely. Statistical models that account for censored data will be employed in appropriate circumstances (e.g., for time-to-event outcomes). Sensitivity analyses, including a tipping-point analysis for the primary endpoint, will be conducted to assess the impact of different assumptions on interpretation of the results. Outlier values will be evaluated for their validity. Suspected invalid data will be queried and corrected in the database prior to statistical analysis.

#### 12.1.2. Post-procedure Endpoints and Measurements

Post-procedure information will be collected at regularly scheduled follow-up examinations as detailed in the clinical study schedule (Table 11.1-1 and Table 11.1-2) and will be summarized using descriptive statistics for continuous variables (e.g., mean, standard deviation,  $n$ , minimum, maximum) and frequency tables or proportions for discrete variables. No inferences are planned on the additional endpoints and, therefore, alpha-adjustments for multiple comparisons will not be used. The Kaplan-Meier product-limit method will be used to determine rates for time-to-event endpoints. Adverse event and SAE rates will be reported.

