### 7.3. *Additional Measurements*

Additional measurements based on the VARC endpoints and definitions (see references and Table 26.2-1 in the Appendix for definitions) will be collected peri- and post-procedure, at discharge or 7 days post-procedure (whichever comes first), 30 days, 3 months, 6 months, and 1, 2, 3, 4, and 5 years post index procedure, unless otherwise specified below. Data will be evaluated on an ITT basis.

- Safety endpoints adjudicated by an independent Clinical Events Committee (CEC):
  - Mortality: all-cause, cardiovascular, and non-cardiovascular
  - Stroke: disabling and non-disabling
  - Composite of all-cause mortality and disabling stroke
  - Myocardial infarction (MI): periprocedural  $\leq 72$  hours post index procedure) and spontaneous ( $>72$  hours post index procedure)

- Bleeding: life-threatening (or disabling) and major
- Acute kidney injury ( $\leq 7$  days post index procedure): based on AKIN System Stage 3 (including renal replacement therapy) or Stage 2
- Major vascular complication
- Repeat procedure for valve-related dysfunction (surgical or interventional therapy)
- Hospitalization for valve-related symptoms or worsening congestive heart failure (NYHA class III or IV)
- New permanent pacemaker implantation resulting from new or worsened conduction disturbances (including left bundle branch block [LBBB] and third degree atrioventricular block)
- New onset of atrial fibrillation and atrial flutter
- Coronary obstruction (periprocedural)
- Ventricular septal perforation (periprocedural)
- Mitral apparatus damage (periprocedural)
- Cardiac tamponade (periprocedural)
- Prosthetic aortic valve malapposition, including valve migration, valve embolization, ectopic valve deployment, or transcatheter aortic valve (TAV)-in-TAV deployment
- Prosthetic aortic valve thrombosis
- Prosthetic aortic valve endocarditis
- Prosthetic aortic valve performance as measured by transthoracic echocardiography (TTE) and assessed by an independent core laboratory, including effective orifice area, mean and peak aortic gradients, peak aortic velocity, and grade of aortic regurgitation
- Functional status as evaluated by the following:
  - 5-m gait speed test (at 1 year compared to baseline)
  - New York Heart Association (NYHA) classification
- Neurological status as determined by the following:
  - National Institutes of Health Stroke Scale (NIHSS) at discharge and 1 year

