**Table 9.2-1: Inclusion Criteria**

Inclusion Criteria	
IC1.	Subject is $\geq 70$ years of age
IC2.	Subject has documented calcific native aortic valve stenosis with an initial aortic valve area (AVA) of $< 1.0 \text{ cm}^2$ (or AVA index of $< 0.6 \text{ cm}^2/\text{m}^2$ ) and either a mean pressure gradient $> 40 \text{ mm Hg}$ or a jet velocity $> 4 \text{ m/s}$ , as measured by echocardiography.
IC3.	Subject has a documented aortic annulus size between $\geq 20$ and $\leq 27 \text{ mm}$ based on pre-procedure diagnostic imaging
IC4.	Subject has symptomatic aortic valve stenosis with NYHA Functional Class $\geq \text{II}$ .
IC5.	Subject is considered high risk for surgical valve replacement based on at least one of the following:
	– STS score $\geq 8\%$ , and/or
IC6.	– Agreement by the heart team (which must include an in-person evaluation by an experienced cardiac surgeon) that subject is at high operative risk of serious morbidity or mortality with surgical valve replacement.
IC6.	Heart team (which must include an experienced cardiac surgeon) assessment that the subject is likely to benefit from valve replacement
IC7.	Subject (or legal representative) understands the study requirements and the treatment procedures, and provides written informed consent.
IC8.	Subject, family member and/or legal representative agree(s) and subject is capable of returning to the study hospital for all required scheduled follow up visits.

Abbreviations: AVA=aortic valve area; NYHA=New York Heart Association; STS= Society of Thoracic Surgeons

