**Table 9.3-1: Exclusion Criteria**

Exclusion Criteria	
EC1.	Subject has a congenital unicuspid or bicuspid aortic valve.
EC2.	Subject with an acute myocardial infarction within 30 days of the index procedure (defined as Q-wave MI or non-Q-wave MI with total CK elevation $\geq$ twice normal

Table 9.3-1: Exclusion Criteria

	in the presence of CK-MB elevation and/or troponin level elevation).
EC3.	Subject has had a cerebrovascular accident or transient ischemic attack within the past 6 months, or has any permanent neurologic defect prior to study enrollment.
EC4.	Subject is on dialysis or has serum creatinine level >3.0 mg/dL or 265 µmol/L.
EC5.	Subject has a pre-existing prosthetic heart valve (aortic or mitral) or a prosthetic ring in any position.
EC6.	Subject has ≥3+ mitral regurgitation, ≥3+ aortic regurgitation or ≥3+ tricuspid regurgitation (i.e., subject cannot have more than moderate mitral, aortic or tricuspid regurgitation).
EC7.	Subject has a need for emergency surgery for any reason.
EC8.	Subject has a history of endocarditis within 12 months of index procedure or evidence of an active systemic infection or sepsis.
EC9.	Subject has echocardiographic evidence of intra-cardiac mass, thrombus or vegetation.
EC10.	Subject has Hgb <9 g/dL, platelet count <50,000 cells/mm  or >700,000 cells/mm  , or white blood cell count <1,000 cells/mm  .
EC11.	Subject is receiving chronic (≥72 hours) anticoagulation therapy (e.g., warfarin, dabigatran, etc.), and cannot tolerate concomitant therapy with aspirin or clopidogrel (subjects who require chronic anticoagulation must additionally be able to be treated with either aspirin or clopidogrel).*
EC12.	Subject has active peptic ulcer disease or gastrointestinal bleed within the past 3 months, other bleeding diathesis or coagulopathy or will refuse transfusions.
EC13.	Subject has known hypersensitivity to contrast agents that cannot be adequately pre-medicated, or has known hypersensitivity to aspirin, all thienopyridines, heparin, nickel, titanium, or polyurethanes.
EC14.	Subject has a life expectancy of less than 12 months due to non-cardiac, co-morbid conditions based on the assessment of the investigator at the time of enrollment.
EC15.	Subject has hypertrophic obstructive cardiomyopathy.

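### Kaplan-Meier with death censored will overstate late non-fatal event rates and cause-specific mortality at 1 to 5 years; cumulative incidence should be reported for these

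*Combined protocol and SAP*

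**What the plan says.** The only statement of method for event rates over time is in section 12.1.2: "The Kaplan-Meier product-limit method will be used to determine rates for time-to-event endpoints". No endpoint is exempted, and the section does not list which endpoints count as time-to-event. It also provides for frequencies or proportions of discrete variables, and it plans no inference on the additional endpoints.

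Section 12.1.1.4 adds a general sentence: "Statistical models that account for censored data will be employed in appropriate circumstances". It speaks of censored data and does not mention death as a competing event. Nothing in the document mentions competing risks or cumulative incidence.

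Section 7.3 collects the additional measurements at visits that include "6 months, and 1, 2, 3, 4, and 5 years post index procedure", unless a shorter period is given for an item. Items with no shorter period include stroke, repeat procedure for valve dysfunction, valve-related hospitalization, endocarditis and valve thrombosis. Spontaneous MI starts only after 72 hours. The time-related valve safety composite in section 7.3 does not have all-cause death as a component. The 1-year VARC efficacy composite counts deaths only after 30 days.

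**The concern.** Subjects are 70 or older and at high surgical risk, and section 12.1.1.3 expects 9.8% to die within 30 days. One exclusion criterion in Table 9.3-1 reads "Subject has a life expectancy of less than 12 months due to non-cardiac, co-morbid conditions". It limits non-cardiac deaths in the first year only, and nothing comparable covers years 1 to 5. Deaths will therefore precede many possible late events.

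Censoring treats the subject as someone who could still have the event later. That is reasonable for a withdrawal and wrong for a death if the aim is to say what fraction of subjects had the event. With deaths censored, 1-KM describes a population in which nobody dies. The late safety and valve-failure rates would then be reported too high, and the gap grows with follow-up. Cardiovascular and non-cardiovascular mortality have the same problem, because each cause removes subjects from risk of the other.

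**Working it through.** The plan states no 5-year event rate and no mortality beyond 30 days, so there is no figure of its own to reproduce. The check compares two quantities under stated assumptions.

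**Direction.** Let h be the event hazard, S_e the survival function for the event alone and S_d that for death. With independent hazards, 1-KM = ∫ h·S_e dt and the cumulative incidence is CIF = ∫ h·S_e·S_d dt. Since S_d is at most 1, 1-KM cannot be smaller than CIF, and it is larger once deaths precede possible events.

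**Size from the document alone.** With 9.8% dead by day 30, 90.2% remain at risk of a later event. For events after day 30, censoring those early deaths multiplies the rate by 1/0.902 = 1.109, about 11% relative, before any later death is counted.

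**Size at 5 years, constant hazards, assumed mortality M.** Take 1-KM = 10%. Then hT = -ln(0.9) = 0.1054 and dT = -ln(1-M), and

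CIF = hT/(hT+dT) × (1 - exp(-(hT+dT))).

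- M = 40%: dT = 0.5108; CIF = 0.1054/0.6162 × (1 - 0.9×0.6) = 0.1710 × 0.46 = 7.9%; ratio 1.27
- M = 50%: dT = 0.6931; CIF = 0.1054/0.7985 × (1 - 0.9×0.5) = 0.1320 × 0.55 = 7.3%; ratio 1.38
- M = 60%: dT = 0.9163; CIF = 0.1054/1.0217 × (1 - 0.9×0.4) = 0.1031 × 0.64 = 6.6%; ratio 1.52

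At 1 year, with assumed mortality of 15% or 25%, the same formula gives ratios of 1.08 and 1.15.

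**Size using the plan's 30-day mortality.** Assume 9.8% mortality by day 30, a constant death hazard from then to 5 years, and a late event hazard of 5% per year starting at day 30 (30/365 year, leaving 4.918 years). Then 1-KM = 1 - exp(-0.05×4.918) = 21.8%. For 5-year mortality of 50%, the late death hazard is ln(0.902/0.5)/4.918 = 0.120 per year, and

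CIF = 0.902 × 0.05/0.170 × (1 - exp(-0.170×4.918)) = 15.0%.

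| Assumed 5-year mortality | 1-KM | CIF | Ratio |
|---|---|---|---|
| 30% | 21.8% | 17.5% | 1.25 |
| 50% | 21.8% | 15.0% | 1.45 |
| 70% | 21.8% | 12.2% | 1.79 |

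At 1 year the gap in these three cases is 0.5 to 0.8 points. A simulation of the middle row (250 subjects, 3,000 datasets) gave means of 21.8% and 15.1%, with 1-KM above CIF in every dataset.

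**Wider range.** The scenarios span 30-day mortality of 3.4% to 20% (the lowest and highest in Table 4.1-1), assumed 5-year mortality of 30% to 70%, and an assumed late event hazard of 2% to 10% per year. For late events the overstatement is 1.6 to 18.3 points at 5 years (ratio about 1.20 to 1.95) and 0.1 to 2.4 points at 1 year (ratio 1.07 to 1.37).

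**Early events.** For an event confined to the first 30 days with 5% net risk and 9.8% mortality, CIF = 0.0513/0.1544 × (1 - 0.95×0.902) = 4.75%, against a 1-KM of 5.0%. Across the scenarios the gap is 0.1 to 0.5 points.

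**Cause-specific mortality.** As an illustration, assume 50% 5-year mortality with the hazard split equally between cardiovascular and non-cardiovascular causes. Each 1-KM is 1 - √0.5 = 29.3%. The two add to 58.6%, although only 50% have died; each cumulative incidence is 25%.

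**The case against.** Four arguments carry weight.

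- **Descriptive use.** The two primary endpoints are assessed at 30 days by a t-test and a z-test. No alpha level, sample size or success criterion uses these rates. For adverse events in a single-arm device study, overstatement is also the cautious direction. All of this stands and limits the importance of the point. Even so, a descriptive rate exists to say how many subjects had the event, and this one would not.
- **Choice of estimand.** Risk in the absence of death can be a legitimate device-focused quantity. But section 12.1.2 speaks only of rates and nowhere says that this quantity is intended.
- **Deferred detail.** Section 12.2 refers to a study-specific statistical analysis plan, whose text is not in the document reviewed, so a competing-risk rule could be there. The method that is written down has no such rule.
- **Assumed size.** Every figure beyond 30 days rests on assumed mortality. In the 10% example the gap is 2.1 to 3.4 points, against a 95% sampling half-width of 1.96 × √(0.1×0.9/250) = 3.7 points. Sampling error is not smaller than the bias there, but the bias always has the same sign.

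A reader might infer that every non-fatal endpoint is materially biased over 5 years. The document does not support that. Section 7.3 limits acute kidney injury to 7 days and several complications to the periprocedural period, and the VARC safety composite is at 30 days. Table 26.2-1 defines new-onset atrial fibrillation as arising during the hospitalization. Section 12.1.2 does not commit every endpoint to Kaplan-Meier. A reader might also infer that any composite containing death can stay on Kaplan-Meier. The 1-year VARC efficacy composite shows otherwise, because deaths by day 30 are not events in it.

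**Conclusion.** The point holds for late non-fatal endpoints reported by Kaplan-Meier at 1 to 5 years, for composites that do not count every death, and for cardiovascular and non-cardiovascular mortality. The direction of the error is certain once deaths are censored. Censoring at death is the default consequence of the named method and is not stated in the document. The size depends on long-term mortality, which the document does not give, and on independent hazards. A relative overstatement of roughly 25% to 80% at 5 years covers the worked cases that use the plan's 30-day mortality, and the excess at 1 year is much smaller. All-cause mortality and composites that count every death, such as death or disabling stroke, are unaffected. The change is worth making, but nothing confirmatory depends on it.

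**What to change.** In section 12.1.2 and the statistical analysis plan:

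1. List which endpoints are analysed as time-to-event.
2. For non-fatal time-to-event endpoints, and for composites that do not count every death, report the Aalen-Johansen cumulative incidence with death as the competing event.
3. For cardiovascular and non-cardiovascular mortality, use the same estimator with the other cause of death competing.
4. Keep Kaplan-Meier for all-cause mortality and for composites that count every death.
5. State how deaths by day 30 are handled in the 1-year VARC efficacy composite: as a competing event, or by a landmark at day 30.

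The cost is plan wording and a standard procedure, with no new data or visits and no change in sample size. Section 12.3.6 already provides for an amended analysis plan approved before the analyses. Comparison with published Kaplan-Meier rates becomes less direct; those curves can be kept as a supplementary display labelled as censoring deaths.
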